234 with reduced length of stay, enhanced quality of life and reduced use of health and social care resources. We anticipate
235 potential gains for individual patients, the wider NHS and society as a whole.

236

237 This study is likely to lead to rapid and important changes in the treatment protocols recommended by the International
238 Liaison Committee on Resuscitation (ILCOR). This organisation was formed in 1992 to provide an opportunity for the
239 major groups engaged in resuscitation worldwide to work together on CPR and emergency cardiovascular care
240 protocols. ILCOR is composed of the American Heart Association (AHA), the European Resuscitation Council (ERC),
241 the Heart and Stroke Foundation of Canada (HSFC), the Australian and New Zealand Committee on Resuscitation, the
242 Resuscitation Council of Southern Africa (RCSA), the Resuscitation Council of Asia (RCA) and the Inter American

243 Heart Foundation (IAHF). As a result it has truly international reach, and its guidelines are almost universally accepted
244 as being the most up to date and effective in the field.

245

246 **3. AIMS AND OBJECTIVES**

247

248 **Aim:**

249 To determine whether the i-gel, a second-generation SAD, is superior to tracheal intubation in non-traumatic OHCA in
250 adults, in terms of both clinical and cost effectiveness.

251

252 **Objectives:**

253 1. To estimate the difference in the primary outcome of modified Rankin Scale (mRS) at hospital discharge (or 30 days
254 post OHCA) between groups of patients managed by paramedics randomised to use either the i-gel or intubation as
255 their initial airway management strategy following OHCA.

256 2. To estimate differences in secondary outcome measures relating to airway management, hospital stay and recovery
257 at 3 and 6 months (see section 4.6.2) between groups of patients managed by paramedics randomised to use either the
258 i-gel or intubation.

259 3. To estimate the comparative cost effectiveness of the i-gel and intubation, including estimating major in hospital
260 resources and subsequent costs (length of stay, days of intensive and high dependency care, etc.) in each group.

261 **4. PLAN OF INVESTIGATION**

[figure not shown]
262

263 **4.1 Trial schema**

264

265 **Figure 1: Trial schema**

266

267

268

269 **4.2 Trial design**

270

271 This is a parallel two-group multi-centre cluster randomised controlled trial (RCT) and accompanying cost-

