500 We will seek consent from survivors (or a consultee according to the requirements of the Mental Capacity Act 2005 if
501 the patient lacks capacity) to collect additional data at hospital discharge and 3 and 6 months after OHCA (depending
502 which consent option the participant chooses-see section 9.7.1). We have chosen a 6-month final follow-up because,
503 whilst there are very few additional deaths between 3 and 6 months, quality of life and functional independence in
504 activities of daily living continue to improve during this time [31].

505

506 *All enrolled patients*

- 507 1. Initial ventilation success, defined as visible chest rise.
- 508 2. Regurgitation/aspiration.
- 509 3. Loss of a previously established airway.
- 510 4. Actual sequence of airway interventions delivered.
- 511 5. Chest compression fraction (one ambulance region only, see below).
- 512 6. Return of spontaneous circulation (ROSC).
- 513 7. Airway management in place when ROSC was achieved or the resuscitation was discontinued.
- 514 8. Economic data regarding expenditure and further healthcare contacts.

515

516 *Patients who survive to admission to hospital (estimated 20% of enrolled patients)*

- 517 9. Length of intensive care stay.
- 518 10. Length of hospital stay.

519

520 *Patients who survive to hospital discharge (estimated 9% of enrolled patients)*

- 521 11. Quality of life (using the EQ-5D) at hospital discharge

522

523 *Patients who survive beyond hospital discharge*

- 524 12. Date of death (if applicable)
- 525 13. Modified Rankin scale at 3 and 6 months following OHCA
- 526 14. Quality of life (using the EQ-5D) at 3 and 6 months following OHCA.

527

528 Good quality, continuous CPR is associated with increased survival and improved neurological outcomes following
529 cardiac arrest [24, 32], and the concept of compression fraction has been developed as a standardised way of
530 measuring and expressing this [33]. The compression fraction is defined as the proportion (or percentage) of
531 resuscitation time without spontaneous circulation during which chest compressions are administered: the higher the
532 compression fraction the better the quality of CPR, and the more likely the patient is to survive [34]. Comparing the
533 compression fraction between the two randomisation arms may help to explain the study findings. Measuring and

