1898 All outcomes listed in Sections 2.3 and 2.4 will be presented as per the template tables **Table T6** to **T8** and
1899 may also be presented graphically. General methods of presentation and assessing intervention effects are
1900 outlined below. For formal comparisons the intubation group will be the reference group. Details specific to
1901 each outcome are described as appropriate. Secondary outcomes 10 to 13 will not be reported in the primary
1902 outcome paper.

Date type	Outcomes
Binary	mRS (at discharge/30days) Initial ventilation success Regurgitation/aspiration Loss of previously established airway Return of spontaneous circulation (ROSC) 72h survival
Categorical	Actual sequence of airway interventions delivered ¹ Airway management in place when ROSC was achieved or resuscitation was discontinued or intervention from A2 paramedic stopped ¹
Continuous	Chest compression fraction

	Duration of ICU stay (presented separately for survivors and patients who die during ICU stay) ¹
	Duration of hospital stay (presented separately for survivors and patients who die during hospital stay) ¹
Time to event	Time from OHCA to when discharge/30 day mRS was assessed ^{1,3} Time to death ² Time to death (up to 72h)
Longitudinal	mRS (at discharge/30days, 3 months and 6 months) EQ-5D index score and visual analogue scale score (at discharge, 3 months and 6 months)

1903 *Note:-*

1904 ¹ These outcomes will be described but not formally compared

1905 ² Time to death will be formally compared in place of length of ICU and hospital stay

1906 ³ This is not a specified outcome but the DMSC raised it as a point of interest.

1907

1908 • **Binary outcomes** will be presented as numbers and percentages of patients in the category of interest.
1909 Outcomes will be compared between intervention groups using logistic regression. The intervention
1910 comparison estimate will be presented as an adjusted odds ratio (OR) with a 95% confidence interval
1911 (95% CI) and p-value. Formal statistical comparisons of treatment effects will only be performed if more
1912 than ten patients in total experience the outcome (with at least one event in each treatment group). .

1913 • **Categorical outcomes** will be presented as numbers and percentages of patients in each category.
1914 Outcomes will be compared between intervention groups using multinomial logistic regression.
1915 Treatment comparison estimates will be presented as adjusted odds ratios (OR) and 95% confidence

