1916 intervals (95% CI). .

1917 • **Continuous outcomes** will be summarised by means and SDs in each treatment group, if distributions
1918 are approximately normal. If distributions are non-normal data will be summarised by the median and
1919 IQR or geometric mean (GM) if a logarithmic transformation provides an approximately normal
1920 distribution. Outcomes will be compared using linear regression. For untransformed data treatment
1921 comparisons will be presented as adjusted differences in means with 95% CI, and for logarithmically
1922 transformed data as adjusted ratios of GMs with 95% CI. Due to the large numbers of trial patients not
1923 expected to survive to 30 days/hospital discharge, a two-part zero-inflated modelling approach will also
1924 be considered for EQ5D visual analogue scale and summary index scores. This will comprise a) an
1925 occurrence model, a logistic regression model for the occurrence of death vs survival; b) intensity model,
1926 a log-linear model for the score, conditional on survival. If it is not possible to fit the model, then an
1927 analysis restricted to those who survive to hospital discharge will be considered.

1928 • **Time to event outcome** time to death will be summarised by the median and IQR in each intervention
1929 group. This will be compared using Cox's proportional hazards or parametric models as appropriate. The
1930 choice of model to use will depend on the distribution of the data. The intervention comparison will be
1931 presented as a hazard ratio (HR) and 95% CI if a proportional hazards model is used or time ratios (TR)
1932 and 95% CI if an accelerated failure time (AFT) model is used. Times will be censored at last contact for
1933 patients known to be alive at that time.

1934 • **Longitudinal outcomes** will be summarised for each time point. Binary and continuous outcomes will
1935 be compared using logistic and linear mixed effects methodologies respectively, with the treatment group
1936 and study design variables (see section 6.2.1) fitted as fixed effects, and patient terms as random effects.
1937 If a time x treatment interaction is not statistically significant at the 10% level an overall treatment effect
1938 will be reported. If the interaction is statistically significant the changes in treatment effect with time will
1939 be described. Different variance/covariance structures will be explored, and the structure that provides

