Duration of ICU stay in all patients admitted to ICU from ED (hours; median, IQR)

HOSPITAL STAY

Survived to hospital discharge
Duration of hospital stay in patients who survived to discharge (days; median, IQR)
Duration of hospital stay in patients who died before discharge (hours; median, IQR)
Duration of hospital stay in all patients admitted to ED (hours; median, IQR)

2075
2076
2077
2078
2079

¹OR=Odds ratio (from logistic or, where marked *, multinomial regression), MD=mean difference, GMR=Geometric mean ratio

[figure not shown]
Table T8 Longitudinal secondary outcomes

	Randomised to intubation (n=XX)		Randomised to i-gel (n=XX)		Overall (n=XX)	
	n	%	n	%	N	%
mRS (0 to 3; good recovery)						
Discharge/30 days						
3 months						
6 months						
Treatment*time interaction						
Overall						OR
	Randomised to intubation (n=XX)		Randomised to i-gel (n=XX)		Overall (n=XX)	
	n	%	n	%	N	%
EQ5D index score (median, IQR)						
Discharge/30 days						
3 months						
6 months						
Treatment*time interaction						
Overall						OR, GMR
EQ5D visual analogue scale score (median, IQR)						
Discharge/30 days						
3 months						
6 months						

Treatment*time interaction	
Overall	OR, GMR

2080
2081
2082
2083
2084
2085
2086
2087

Figure F7 Subgroup analyses (example for one subgroup analysis: event witnessed by ambulance staff)

2088
2089

Table T9 Unexpected serious adverse events

		Received Intubation first (n=XX)		Received i-gel first (n=XX)	
		n	%	n	%
Number of patients experiencing one or more SAEs					
Number of events					
Brief description of events					
Timing of events	Pre-surgery Post-surgery but pre-discharge Post-discharge				
Maximum intensity	Mild Moderate Severe				
Reason event classified as SAE	Resulted in death Is/was life threatening Resulted in persistent or significant disability/incapacity Prolonged ongoing hospitalisation/ caused hospitalisation Other				
Relatedness to intervention	Possibly related Probably related Definitely related				

2090
2091
2092
2093

Table T10 Details of unexpected serious adverse events

Study ID=	Intervention randomised to=	Interventions received=	Patient withdrawn from study (and when)=
OHCA date=	Hospital discharge date (if applicable)=	Death date (if applicable)=	Timing of SAE= Post-intervention but pre-discharge/ Post-discharge
Brief description of event=	Location=	Maximum intensity=	Relatedness=
SAE start date/time=	SAE resolution date/time=	Event resulted in death=	Event was life threatening=

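### A 10% time-by-treatment pre-test decides whether any treatment effect at 3 or 6 months is reported for mRS and EQ-5D, although Objective 2 asks for differences at those times

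*Protocol*

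**What the plan says.** Objective 2 (protocol section 3, repeated in SAP section 2.2) is "To estimate differences in secondary outcome measures relating to airway management, hospital stay and recovery" at 3 and 6 months. Secondary outcomes 12 and 13 in SAP section 2.4 are mRS and EQ-5D at 3 and 6 months. Protocol section 4.6.2 justifies the final visit by saying that, "whilst there are very few additional deaths between 3 and 6 months, quality of life and functional independence in" daily living go on improving over that period.

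The data-type table in SAP section 6.2.2 lists two longitudinal outcomes, each with three time points: "mRS (at discharge/30days, 3 months and 6 months") and "EQ-5D index score and visual analogue scale score (at discharge, 3 months and 6 months"). Such outcomes "will be summarised for each time point. Binary and continuous outcomes will" be compared by logistic or linear mixed models. The reporting rule then reads: "If a time x treatment interaction is not statistically significant at the 10% level an overall treatment effect" "will be reported. If the interaction is statistically significant the changes in treatment effect with time will" be described.

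Table T8 has the same layout. For each outcome it gives a summary by arm at each of the three times, a row for "Treatment*time interaction", and one overall estimate (OR for mRS; OR and GMR for the EQ-5D scores).

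**The concern.** What is reported depends on a significance test run on the same data. If the interaction has p >= 0.10, one effect averaged over three times is given and no adjusted 3- or 6-month effect with an interval is planned. If p < 0.10, the change over time is to be described, but the text does not commit to estimates and intervals at each time even then.

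Failing to reject equality of the effects is not evidence that they are equal. The SAP gives no margin for judging them similar and no power for the interaction test. The group that can supply longitudinal mRS is small compared with the trial as a whole. If the two airway strategies differ more in later recovery than at discharge, the overall effect dilutes the later difference, and the reader is left with crude arm-level figures at 3 and 6 months without an adjusted contrast or a measure of its uncertainty.

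**Working it through.** **Size of the longitudinal mRS group.** The total is 9,070 (protocol section 4.7). It reproduces closely: 8% v 10%, two-sided 5%, 90% power gives 4,401 per group with continuity correction (stated 4,400). The design effect 1 + (7 - 1) x 0.005 = 1.03 gives 4,400 x 1.03 = 4,532 (stated 4,535). Survival to discharge is put at 9% (section 4.6.2) and consent to follow-up at 86% of those discharged (section 5.12).

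- Survivors: 9,070 x 0.09 = 816
- Consenting: 816.3 x 0.86 = 702, or 351 per arm

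This is an upper figure, because Population 5 needs consent to active follow-up and some consenting patients may choose the passive option. I therefore also used 300 per arm. The figure applies to mRS only; SAP 5.3 and 6.2.2 allow deaths to enter the EQ-5D model.

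**Assumptions not in the documents.** Good recovery in control survivors of 80%, 85% and 88% at discharge, 3 and 6 months; exchangeable latent-normal correlation of 0.7 or 0.85; complete data; no clustering. The test is a 2-df Wald test of equal log ORs at the 10% level. When it does not reject, the overall effect is the equally weighted mean of the three log ORs.

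**True ORs for a difference of 0, 2.5 and 5 points.**

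- Discharge, 80% v 80%: 1.00 (log 0)
- 3 months, 85% v 87.5%: 7.000/5.667 = 1.24 (log 0.211)
- 6 months, 88% v 93%: 13.286/7.333 = 1.81 (log 0.594)
- Mean log OR: (0 + 0.211 + 0.594)/3 = 0.268, so OR 1.31 before any selection on the test result

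**Simulated behaviour of the rule (6,000 replicates per row).**

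| Per arm | Correlation | Test misses | Mean pooled OR when missed | Pooled CI covers 1.81 when missed | Miss and CI excludes 1.81 |
|---|---|---|---|---|---|
| 351 | 0.70 | 35% | 1.25 | 44% | 20% |
| 351 | 0.85 | 27% | 1.23 | 47% | 14% |
| 300 | 0.70 | 40% | 1.25 | 51% | 20% |
| 300 | 0.85 | 33% | 1.24 | 54% | 15% |

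The last column is the miss rate times (1 - coverage), for example 0.349 x (1 - 0.438) = 0.196. Separate runs move the miss rate by a point or two, hence the range of 25-41%.

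**Smaller change: 0, 1 and 2 points.** The test misses it about 80-83% of the time, but the pooled interval still covers the 6-month OR of 1.23 about 90% of the time. A separate 6-month estimate would say little here. With 351 per arm, SE = sqrt(1/(351 x 0.88 x 0.12) + 1/(351 x 0.90 x 0.10)) = 0.242, so the expected 95% CI is about 0.76 to 1.97.

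**Constant effect.** By construction the 10% test fails to reject in about 90% of trials. The overall effect is then the right quantity at every time.

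**A second set of assumptions.** With a flat 70% or 80% base rate, correlation 0.3-0.7 on the binary scale, 351 per arm and inverse-variance pooling, a difference of 0, 5 and 5 points is missed in 23-65% of trials. Later ORs of 1.29 (70% base) or 1.42 (80% base) are pooled to about 1.16-1.18 or 1.21-1.24. A jump of 0, 10 and 10 points is nearly always detected (power 88% or more).

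**The case against.** The rule is set in advance and uses a lenient 10% level, against 5% elsewhere in the SAP. Protocol section 6.1 already calls for a repeated-measures analysis of mRS, and an overall effect to 6 months is a coherent summary. Arm-level results appear at every time, so crude differences can be seen, and the SAP nowhere says that a non-significant test proves a constant effect. The scenarios above all assume no effect at discharge and growth later, which is the pattern that the rule handles worst. The simulated ORs are marginal, whereas a model with patient random effects gives conditional ones. Only secondary outcomes are involved, and SAP 6.2.2 keeps outcomes 10 to 13 out of the primary paper. All of this stands, and it limits the size of the point. It does not supply the missing 3- and 6-month estimates.

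Three stronger readings are tempting and are not supported:

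- A reader might infer that pooling with discharge pulls the longer-term estimate towards the primary result. The primary analysis uses Population 1a, all trial patients with deaths scored 6. The longitudinal mRS uses Population 5, consenting survivors. They share a time point but are different contrasts. For EQ-5D, discharge is a listed secondary outcome in its own right.
- A reader might infer that Objective 2 goes unanswered whenever the test is non-significant. If the effect is truly constant, the overall effect is the 3- and 6-month effect, estimated more precisely.
- A reader might infer that 6 months should be the main longer-term estimate. Neither Objective 2 nor the outcome list ranks it above 3 months.

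**Conclusion.** The point holds as a mismatch between the objective and the reporting rule. Objective 2 and outcomes 12 and 13 ask for differences at 3 and 6 months, while SAP 6.2.2 and Table T8 plan no effect with an interval at those times when p >= 0.10. That mismatch rests on the text alone.

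Its practical size rests on the assumed recovery rates, correlations and delayed-effect pattern, and is moderate. For a change of 0, 2.5 and 5 points, a clearly misleading interval arises in roughly one trial in five to one in seven. For small changes the loss is slight, and large changes are usually detected. The primary analysis and the sample size are not affected. It is worth correcting because the correction costs almost nothing.

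**What to change.** Replace the rule in SAP 6.2.2 with wording such as: treatment effects with 95% CIs will be reported at discharge/30 days, 3 months and 6 months from the longitudinal model, whatever the interaction p-value; the overall effect and the interaction p-value will be reported alongside. Add the corresponding estimate rows to Table T8 for mRS, the EQ-5D index and the EQ-5D visual analogue score.

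This needs no new data and no change in sample size; the estimates come from the model with its interaction term, which is fitted anyway for the test. The cost is that the time-specific intervals are wider than the pooled one, which remains in the table.

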1331 The local principal Investigators will be required to allow access to study documentation or source data on request for
1332 monitoring visits and audits performed by the Sponsor or CTEU Bristol or any regulatory authorities. They will be
1333 required to read, acknowledge and inform their trial team of any amendments to the trial documents approved the REC
1334 that they receive and ensure that the changes are complied with.
1335

1336

1337 **10.4 Monitoring by sponsor**
1338

1339 The study will be monitored and audited in accordance with the Sponsor's policy, which is consistent with the
1340 Research Governance Framework and the Medicines for Human Use (Clinical Trials) Regulations 2004. All study
1341 related documents will be made available on request for monitoring and audit by the sponsor (or CTEU Bristol if they
1342 have been delegated to monitor see 7.2.2), the relevant REC and for inspection by other licensing bodies.
1343

1344

1344 **10.5 Indemnity**
1345

1346 This is an NHS-sponsored research study. For NHS sponsored research HSG(96)48 reference no. 2 refers. If there is
1347 negligent harm during the clinical trial when the NHS body owes a duty of care to the person harmed, NHS Indemnity
1348 covers NHS staff, medical academic staff with honorary contracts, and those conducting the trial. NHS Indemnity does
1349 not offer no-fault compensation and is unable to agree in advance to pay compensation for non-negligent harm. Ex-
1350 gratia payments may be considered in the case of a claim.
1351

1352

1352 **10.6 Clinical Trial Authorisation**
1353

1354 The intervention is not classed as an investigational medicinal product as the I-gel device is CE marked and is being
1355 used with its license, therefore a Clinical Trial Authorisation from the MHRA is not required.
1356

1357

1358 **11. DATA PROTECTION AND PARTICIPANT CONFIDENTIALITY**

1359

1360 **11.1 Data protection**

1361

1362 Data will be collected and retained in accordance with the UK Data Protection Act 1998.

1363

1364

1365 **11.2 Data handling, storage and sharing**

1366

1367 **11.2.1 Data handling**

1368

1369 Data will be entered onto a purpose designed database and data validation and cleaning will be carried out throughout
1370 the trial. Standard operating procedures (SOPs) for database use, data validation and data cleaning will be available
1371 and regularly maintained.

1372

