1678 or second attempt¹.
- 1679 2. Regurgitation/aspiration.
- 1680 3. Loss of a previously established airway.
- 1681 4. Actual sequence of airway interventions delivered.
- 1682 5. Chest compression fraction (two ambulance regions only, added part way through the trial)
- 1683 6. Return of spontaneous circulation (ROSC)*.
- 1684 7. Airway management in place when first ROSC was achieved or the resuscitation was discontinued.
- 1685

1686 Patients who survive to admission to hospital (estimated 20% of enrolled patients):

- 1687 8. Length of intensive care stay.
- 1688 9. Length of hospital stay.

¹ Note: chest rise and ETCO₂ is the definition on the CRF, but ETCO₂ is not included in the definition given in the protocol. Also, the protocol does not state whether success should be based on the first attempt only or the first or second attempt.

1689	
1690	Patients who survive to hospital discharge and consent to active follow-up (estimated 9% of enrolled
1691	patients):
1692	10. Quality of life (using the EQ-5D) at hospital discharge.
1693	
1694	Patients who survive beyond hospital discharge and consent to active follow-up:
1695	11. Time to death or last follow-up
1696	12. Modified Rankin score at 3 and 6 months following OHCA
1697	13. Quality of life (using the EQ-5D) at 3 and 6 months following OHCA.
1698	* note: this outcome includes both ROSC during advanced airway management attempts carried out by an
1699	AIRWAYS-2 paramedic and on ED arrival for those patients conveyed to ED
1700	2.5 Changes to the study objectives during the course of the study
1701	N/A
1702	2.6 Changes to the study outcomes during the course of the study
1703	There have been no outcomes added or removed, but outcomes that were not clearly defined in the protocol
1704	have been reviewed and precise definitions have been agreed. These include definitions for secondary
1705	outcomes 1 to 7, the addition of time to death as a more informative means of comparing length of ICU and
1706	hospital stays and two analyses of survival at 72h (as binary and time to event outcomes) . Definitions are
1707	given in Section 5.
1708	

1709 **3. STUDY POPULATION**

1710 The study population is patients aged 18 or over experiencing a non-traumatic OHCA. Enrolled patients must
1711 be attended by an A2 paramedic who is first or second at the patient's side and resuscitation must be

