1791 analyses on an intention to treat basis (ITT). For patients who do not wish for their previously collected data
1792 to be used, we will exclude all data collected after the point of consent (i.e. ward movements, EQ-5D and
1793 follow-up data) from any analyses.

1794 Data on all withdrawals is captured on a specific case report form (CRF), and will be tabulated by allocation
1795 of the enrolling paramedic (**Table T3**).

1796 **3.7 Analysis populations**

- 1797 • **Population 1a:** The analysis population for the primary outcome (mRS at discharge/30-days) is all
1798 patients who receive resuscitation, are attended by an A2 paramedic and meet the eligibility criteria,
1799 i.e. all trial patients. This is also the analysis population for outcome 5 (chest compression fraction),
1800 but limited to two trusts and starting partway through the trial.

- 1801
- 1802
- 1803
- **Population 1b:** The analysis population for the second component of secondary outcome 6 (ROSC on ED arrival) is all patients who receive resuscitation, are attended by an A2 paramedic, meet the eligibility criteria and were conveyed to ED.
- 1804
- 1805
- 1806
- 1807
- **Population 2:** The analysis population for secondary outcomes 1 to 4, 6 and 7 (airway management details, but only covering ROSC during advanced airway management by A2 paramedic for outcome 6) is all trial patients who received at least one advanced airway management attempt by the enrolling A2 paramedic.
- 1808
- 1809
- **Population 3:** The analysis population for secondary outcome 8 (length of initial ICU stay) is all trial patients who were admitted to ICU.
- 1810
- 1811
- 1812
- **Population 4:** The analysis population for secondary outcome 9 (length of hospital stay) is all trial patients admitted to hospital who did not refuse consent (i.e. patients who either consent to active or passive follow-up or who die prior to approach).
- 1813
- 1814
- 1815
- 1816
- 1817
- **Population 5:** The analysis population for secondary outcomes 10 and 13 (EQ-5D health scores and state scores) and secondary outcomes 11 and 12 (time to death after discharge and mRS during follow-up) is all trial patients who consent to active follow-up, survive to 30 days/hospital discharge and provide relevant data for at least one of the three time points (30 days/hospital discharge, 3 months and/or 6 months).
- 1818
- 1819
- 1820

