1940 the best fit in terms of information criteria such as AIC, BIC and likelihood ratio tests will be used.

1941 **6.2.3 Statistical significance**

- 1942 For hypothesis tests two-tailed p-values < 0.05 are considered statistically significant.
- 1943 **6.2.4 Model assumptions**
- 1944 For all methods outlined underlying assumptions will be checked using standard methods, e.g. residual plots,
1945 tests for proportional hazards, etc. If assumptions are not valid then alternative methods of analysis will be
1946 sought. If outlying observations are found which mean models do not fit the data adequately, such
1947 observations will be excluded from the main analyses and comments made in footnotes.
- 1948 **6.2.5 Subgroup analyses**
- 1949 Two subgroup analyses for the primary outcome are specified in the protocol: Utstein comparator group vs
1950 non-comparator group and arrest witnessed by ambulance staff or not (**Figure F7**).
- 1951
- 1952 Due to concerns regarding ventilation success raised during the trial, a subgroup analysis of the primary
1953 outcome comparing patients whose i-gel or intubation airway management attempt(s) were or were not
1954 ‘successful’ during the first and/or second attempt (see section 5.2 for definition) will also be performed. This
1955 analysis will be performed per-protocol and as such will only include patients who received at least one
1956 advanced airway management attempt using an i-gel and/or intubation tube.
- 1957
- 1958 Subgroup effects will be fitted by adding a “sub-group x intervention” interaction term to the analysis model.
- 1959 **6.2.6 Sensitivity analyses**
- 1960 For the primary outcome, the following sensitivity analyses will be performed:
- 1961
 - ITT analysis including only patients who received at least one advanced airway management attempt
1962 using an i-gel and/or intubation tube.
 - Per-protocol analysis including only patients who received at least one advanced airway management
1963 attempt using an i-gel and/or intubation tube (see section 6.2.5 for additional sub-group analysis for
1964 this outcome).
 - ITT analysis including all patients who were attended by an AIRWAYS-2 paramedic but not
1965 resuscitated.
- 1966
- 1967
- 1968 **6.2.7 Missing data**
- 1969 In all tables missing data will be indicated by footnotes. If the amount of missing data differs substantially
1970 between treatment groups potential reasons will be explored.
- 1971 Missing predictors:

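### SAP 6.2.4 removes outlying values from the main analyses without requiring a confirmed error, and plans no analysis that keeps them

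*Protocol*

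**What the plan says.** SAP 6.2.4 (Model assumptions) covers all the methods in the plan and contains two separate instructions.

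- On assumptions: "If assumptions are not valid then alternative methods of analysis will be" sought.
- On outliers: "If outlying observations are found which mean models do not fit the data adequately, such" "observations will be excluded from the main analyses and comments made in footnotes".

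Other places that bear on this:

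- SAP 6.2.6 opens with "For the primary outcome, the following sensitivity analyses will be performed" and lists three: ITT restricted to patients with an i-gel or intubation attempt, a per-protocol analysis of such patients, and ITT adding attended patients who were not resuscitated. None concerns a secondary outcome, and none restores excluded values.
- SAP 3.7 defines Population 1a as "i.e. all trial patients. This is also the analysis population for outcome 5 (chest compression fraction"), limited to two trusts and starting part way through.
- SAP 2.4 lists "Chest compression fraction (two ambulance regions only, added part way through the trial"), and SAP 6.2.2 says of continuous outcomes: "Outcomes will be compared using linear regression".
- Protocol 11.2.1 says that "data validation and cleaning will be carried out throughout" the trial. SAP 6.2.4 does not refer to it.

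**The concern.** A value can be extreme and correct. Under 6.2.4 such a value leaves the main analysis because of what it is, after randomisation and after a model has been fitted. That is selection on the outcome, and it sits badly with the all-patient population in SAP 3.7 and the intention-to-treat commitment in SAP 6.2.2. With no criterion for an outlier, the decision is also left to judgement once the fit has been seen.

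Compression fraction is the clearest case. It is the only formally compared outcome in the Continuous class of SAP 6.2.2; the ICU and hospital stays in that class are only described. Protocol 4.6.2 proposes fewer interruptions to CPR as the way a supraglottic device might help, and protocol 9.3 says interruptions may be more common with intubation. The values most likely to be called outlying, very low fractions, are therefore the ones that would carry the mechanism. Removing them would understate an i-gel advantage; it would not create a false one.

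EQ-5D scores and time to death fall under the same sentence. They are bounded or censored, so the rule has less to act on.

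**Working it through.** **Reading the text**

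1. *Is exclusion a last resort?* The sentence on alternative methods is triggered by invalid assumptions. The next sentence gives outliers their own action and does not require other methods to be tried first.
2. *Is it limited to errors?* No. Cleaning under protocol 11.2.1 is general and exclusion does not depend on it, so a value that passes validation can still be dropped.
3. *Does any analysis keep the values?* None in SAP 6.2.6. SAP 6.2.7 deals with missing data only.
4. *Do other provisions absorb outliers?* SAP 6.2.2 uses medians for summary, but the comparison is by linear regression. The optional log transformation stretches a low tail, so it does not help with very low fractions.

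**Illustrating the size**

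The documents give no mean, SD, number per arm or cut for compression fraction, so every input is assumed: mean 82%; SD 7 or 12; low values in 5% of intubation and 1% of i-gel patients; values clipped to 0–100; exclusion of any residual beyond 3 pooled SD unless stated. Each scenario was simulated 4,000 times. Coverage is the share of 95% intervals after exclusion that contain the all-patient difference.

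*Check by hand (SD 7, 30-point drop, clipping ignored).*

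- All-patient difference: (0.05 − 0.01) × 30 = 1.2 points.
- Arm variances: 49 + 0.05 × 0.95 × 900 = 91.75 and 49 + 0.01 × 0.99 × 900 = 57.91. Pooled SD = √74.83 = 8.65; cut = 3 × 8.65 = 25.95.
- Intubation: low values centre 28.5 below the arm mean, so Φ((28.5 − 25.95)/7) = Φ(0.364) = 0.642 of them are dropped, which is 3.2% of patients.
- i-gel: Φ((29.7 − 25.95)/7) = Φ(0.536) = 0.704 are dropped, which is 0.7% of patients.
- The low values that remain lie on average 30 − 7 × 1.043 = 22.7 points down (intubation) and 30 − 7 × 1.167 = 21.8 points down (i-gel). Difference after exclusion: 0.0179 × 22.7/0.968 − 0.0030 × 21.8/0.993 = 0.42 − 0.065 ≈ 0.35 points.

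The simulation gives 1.22 to 0.37, with the same exclusion rates.

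| Scenario | Per arm | SD 7: difference, coverage | SD 12: difference, coverage |
|---|---|---|---|
| Pauses of 1–3 min over 15–90 min | – | 0.20 → 0.19, 95% | 0.19 → 0.19, 95% |
| 20-point drop | 300 | 0.79 → 0.50, 90% | 0.76 → 0.65, 94% |
| 30-point drop | 50 | 1.21 → 0.50, about 90% | see note |
| 30-point drop | 150 | 1.18 → 0.38, 81% | see note |
| 30-point drop | 300 | 1.22 → 0.37, 70% | see note |
| 30-point drop | 600 | 1.20 → 0.36, 51% | see note |
| 40-point drop | 300 | 1.61 → 0.16, 32% | 1.58 → 0.76, 84% |
| 30-point drop, 4-SD cut | 300 | 1.20 → 0.94, 91% | 1.19 → 1.12, 94% |
| 30-point drop, tails 10% vs 2% | 300 | 2.40 → 1.51, 69% | 2.37 → 1.94, 91% |

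Note: with SD 12 and a 30-point drop, about 1.19 → 0.82 to 0.88 across 50 to 600 per arm, coverage 91% to 94%.

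*Equal tails (5% in both arms, 30 points, 300 per arm).* There is no bias, but the interval narrows from 3.06 to 2.59 points (SD 7) or from 4.18 to 3.98 (SD 12), with coverage about 93%.

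*How plausible is a 30-point drop?* It means 0.30 × 15 = 4.5 minutes without compressions in a 15-minute attempt, or 0.30 × 90 = 27 minutes in a 90-minute one (range from protocol 5.4). The large effects need short attempts with long gaps.

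**The case against.** The text itself is hard to dispute, so the case against concerns reach, likelihood and the numbers.

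- *Reach.* Binary outcomes have no outliers in the usual sense, and length of stay is not formally compared. EQ-5D is bounded, and time to death is censored at 183 days; a Cox fit uses only the ordering of times. What remains is essentially one explanatory secondary outcome in two regions. This stands, and it keeps the point minor.
- *Trigger.* A value must be outlying and must also make the fit inadequate. With several hundred patients per arm, a comparison of means may tolerate a few percent of low values, so the rule may never fire. One can also read the sentence on alternative methods as coming first. The first part stands: the harm is conditional. On the second, the text does not state that order, and the wording on outliers is mandatory.
- *Simulation.* It applies an automatic 3- or 4-SD cut, which the SAP does not contain, with no check of fit, no paramedic effect and no design factors. This stands. The figures illustrate what removing such values does and do not forecast the trial. The scenario tied to the protocol's 15–90 minutes shows no effect, and even that range is the pre-hospital phase, not the time without circulation over which compression fraction is defined.
- *Visibility.* Exclusions are footnoted, so a reader could ask for the full analysis. True, but a footnote does not supply the all-patient estimate.
- *Conflict with SAP 3.7.* That section says who enters the analysis, while 6.2.4 is a contingency for model diagnostics, and neither mentions the other. Tension is the right word; flat contradiction would be too strong.

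**Conclusion.** The concern holds as a minor one. SAP 6.2.4 fixes a rule that removes outcome values without a confirmed error and plans no analysis that keeps them. The primary conclusion is not at risk.

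For compression fraction the direction of harm is clear only if genuine low values are more common in one arm. If that arm is intubation, the difference shrinks towards zero. The size cannot be derived from the documents. Under the assumed inputs it runs from nothing (short pauses), through modest (SD 12 or a 4-SD cut with a 30-point drop), to loss of most of the difference (SD 7, drops of 30 to 40 points, 3-SD cut). With equal tails there is no bias, only an interval that is slightly too narrow.

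**What to change.** Replace the last sentence of SAP 6.2.4 with:

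> No valid observation will be excluded from the main analysis because it is outlying; only confirmed recording or device errors will be corrected or set to missing. If outliers affect model fit, robust or bootstrap inference will be used, and any analysis excluding outlying values will be reported only as a sensitivity analysis, with numbers excluded by arm.

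The cost is one sentence in the SAP and a robust or bootstrap option in the analysis code. The only statistical downside is a possibly wider interval when genuine extreme values are kept.
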